6.6.2 Treatment Allocation to the Subject

Treatment numbers will be allocated by dose.

The enrollment will be performed to ensure equal distribution of the population within the age strata (subjects 18-45 years of age versus subjects 50-70 years of age).

Allocation of the subject to a study group at the study center will be performed using SBIR. As the study will enroll 2 age groups sequentially through 4 steps (Step 1: 18-45 years of age and Steps 2, 3, and 4: 50-70 years of age), the steps will be considered as stratification factors with a specific size and group ratio at each step (Step 1: 20 subjects with ratio 1:1 between CDIFF Ag

and placebo alone; Step 2: 20 subjects with ratio 1:1 between CDIFF Ag and placebo alone, Step 3: 30 subjects with ratio 1:1:1 between CDIFF Ag, CDIFF Ag + AS01_B and placebo; Step 4: 70 subjects with ratio 5:7:2 between CDIFF Ag, CDIFF Ag + AS01_B and placebo). Within the 18-45 years age group, the randomization algorithm will use a minimization procedure accounting for gender (female, male), while within the 50-70 years age group, the randomization algorithm will use a minimization procedure accounting for age (50-59 years of age, 60-70 years of age) and gender (female, male). Minimization factors will have equal weight in the minimization algorithm. A minimum of 20% of each minimization factor category will be required to allow enrolling all categories within each minimization factor (refer to Section 8.11 for study procedures to be considered during special circumstances).

After obtaining the signed or witnessed/thumb printed and dated informed consent form (ICF) from the subject and having checked the eligibility of the subject, the study staff in charge of the vaccine administration will access SBIR. Upon providing the age (subjects 18-45 years of age versus subjects 50-70 years of age), the gender, and the subject identification number, the randomization system will determine the study group and will provide the treatment number to be used for the first dose.

The number of each administered treatment must be recorded in the eCRF on the Vaccine Administration screen.

When SBIR is not available, please refer to the SBIR user guide or the SPM for specific instructions.

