9.3 Populations for Analyses

For purposes of analysis, the analysis sets in [Table 24](#) are defined.

Table 24 Analysis Sets

Analysis Set	Description
Enrolled Set	All subjects who signed the ICF.
Exposed Set	
All subjects who have received at least 1 dose of the study vaccine. The allocation in a group is done in function of the administered treatment.
 
 Unsolicited Safety Set Solicited Safety Set Subcohort Exposed Set
Full analysis Set	All subjects who received at least 1 dose of the study treatment and have postvaccination immunogenicity data.
Per-protocol Set	
All subjects who received at least 1 dose of the study treatment to which they are randomized and have postvaccination data (Full Analysis Set) minus subjects with protocol deviations that lead to exclusion. The protocol deviations leading to exclusion of the subjects will be detailed in the SAP.
 
Three Per-protocol Sets for analysis of immunogenicity will be derived.
 
 Per-protocol Set for analysis of immunogenicity at Day 61 (1-month post dose 2) Per-protocol Set for analysis of immunogenicity at Day 180 Per-protocol Set for analysis of immunogenicity at Day 390
Subcohort Per-protocol Set	
 Subcohort Per-protocol Set for analysis of immunogenicity at Day 521 in the Subcohort Set Subcohort Per-protocol Set for analysis of immunogenicity at Day 670 in the Subcohort set

AE = adverse event; ICF = informed consent form; SAP = statistical analysis plan

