9.4.2 Safety Analyses

9.4.2.1 Primary Analyses

The primary analysis will be performed on the Exposed Set.

The percentage of subjects with at least 1 local AE (solicited and unsolicited), with at least 1 general AE (solicited and unsolicited) and with any AE during the 7-day or the 30-day follow-up period will be tabulated with exact 95% CI after each vaccination and overall. The percentage of doses followed by at least 1 local AE (solicited and unsolicited), by at least 1 general AE (solicited and unsolicited) and by any AE will be tabulated, overall vaccination course, with exact 95% CI. The same computations will be done for Grade 3, any AEs considered related to vaccination and any Grade 3 AEs considered related to vaccination.

The percentage of subjects/doses reporting each individual solicited local and general AE during the 7-day follow-up period will be tabulated with exact 95% CI as follows:

- Over the 2 or 3 doses, the percentage of subjects with the symptom and its exact 95% CI.
- Over the 2 or 3 doses, the percentage of doses with the symptom and its exact 95% CI.
- At each study dose (visit), the percentage of subjects with the symptom and its exact 95% CI.

Occurrence of fever will be reported per 0.5°C cumulative increments as from $\geq 38^{\circ}\text{C}$ as well as the occurrence of fever $>40^{\circ}\text{C}/104^{\circ}\text{F}$ with causal relationship to the study treatment.

The verbatim reports of unsolicited symptoms will be reviewed by a physician and the signs and symptoms will be coded according to the Medical Dictionary for Regulatory Activities (MedDRA). Every verbatim term will be matched with the appropriate preferred term. The percentage of subjects with unsolicited AEs within 30 days after any doses with its exact 95% CI will be tabulated by group and by MedDRA preferred term. Similar tabulation will be done for Grade 3 unsolicited AEs, for unsolicited AEs that resulted in a medically attended visit, for Grade 3 and causally related unsolicited AEs and for unsolicited AEs causally related to vaccination.

The number of subjects who experienced at least 1 SAE or any AE of specific interest (pIMD) during the entire study period will be reported.

For each group and for each hematology, biochemistry, and urinalysis parameter:

- The percentage of subjects having hematology, biochemistry, and urinalysis results below or above the local laboratory normal ranges will be tabulated by timepoint.

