### 5.2. EXPOSED SET

The exposed set will contain all subjects who have received at least 1 dose of study treatment and will be analyzed according to treatment received. Subjects with invalid informed consent or fraudulent data will be excluded from this cohort. Subjects in this population will be used for demographic and dosing summaries.

The allocation in a group is done in function of the first administered treatment:

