#### 6.4.1. ATTRIBUTING EVENTS TO VACCINE DOSES

The dose relative to an event is the most recent study dose given to a subject prior to the start of a given event. For example, if the start date of an adverse event is between Dose 1 and Dose 2, the relative dose will be Dose 1.

If an event starts on the same day as a study dose, the relative dose will be derived from the additional information provided in the CRF using the contents of the flag indicating if the event occurred before or after vaccination. If 'after vaccination' is selected, the relative dose for the event will be the one administered on the start day of the event. If 'before vaccination' is selected, the relative dose for the event will be the dose prior to this one. Where applicable, the event will be classified as "pre-treatment".

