## 11.2. DEVIATIONS RELATED TO IMMUNOGENICITY ANALYSIS

Changes to the procedures or events, which may impact the quality of the immunogenicity data, will be considered significant protocol deviations and will be described within the clinical study report. These changes or events will include any circumstances that will alter the evaluation of the immunogenicity results. Examples include, but may not be limited to, sample processing errors that lead to inaccurate immunogenicity results, and/or inaccurate dosing.

Subjects may be eliminated from the per-protocol Set for analysis of immunogenicity if, during the study, they incur a condition that has the capability of altering their immune response or are confirmed to have an alteration of their initial immune status. Subjects may also be eliminated from the per-protocol set based on usage of certain concomitant medications/products/vaccines as described in Section 6.8.2 of the protocol. Such scenarios will be discussed by the study team and decision to exclude a subject and/or data from the Per-protocol analysis set (Day 61, Day 180 and Day 390) or subcohort per-protocol analysis set (Day 521 and Day 670) will be taken on a case-by-case basis.

Other deviations (not a comprehensive list) leading to elimination from the per-protocol set are:

- Invalid informed consent
- Fraudulent data
- randomization code broken
- dose volume insufficient
- vaccination not according to protocol
- vaccine dose storage conditions (temperature deviation)
- vaccine administered out of expiry date
- violation of inclusion/exclusion criteria
- interval between doses
- interval between post vaccination blood sampling and previous dose
- two doses not in the same treatment group
- concomitant infection related to study vaccine or not related to study vaccine that may alter the immune response
- serology result at post vaccination dose 2 not available for all assays (blood sample not available or result not available)

Protocol Deviation Management Plan (PDMP) describes the complete list of elimination codes that could lead to exclusion from the per-protocol set.

---

Document:	\\\usadc-nas01a\cp_ops\PROJECTS\Glaxo SmithKline\GSK208109_BZA47109\SAP		
Author:	PPD	Version Number:	3.0
		Version Date:	27SEP2021

Template No: CS\_TP\_BS016 – Revision 5  
Effective Date: 01Apr2018

Reference: CS\_WI\_BS005

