### 16.1. ADVERSE EVENTS

Adverse Events (AEs) will be coded using Medical Dictionary for Regulatory Activities (MedDRA) central

---

Document:	\\usadc-nas01a\cp_ops\PROJECTS\Glaxo SmithKline\GSK208109_BZA47109\SAP		
Author:	PPD [REDACTED]	Version Number:	3.0
		Version Date:	27SEP2021

Template No: CS\_TP\_BS016 – Revision 5  
Effective Date: 01Apr2018

Reference: CS\_WI\_BS005

---

coding dictionary, Version 22.0.

The percentage of subjects with at least 1 local AE (solicited and unsolicited), with at least 1 general AE (solicited and unsolicited) and with any AE during the 7-day or the 30-day follow-up period will be tabulated with exact 95% CI after each vaccination and overall.

The percentage of doses followed by at least 1 local AE (solicited and unsolicited), by at least 1 general AE (solicited and unsolicited) and by any AE will be tabulated, overall vaccination course, with exact 95% CI. The same computations will be done for Grade 3, any AEs considered related to vaccination, any Grade 3 AEs considered related to vaccination and any AEs resulting in a medically attended visit.

The percentage of subjects/doses reporting each individual solicited local and general AE during the 7-day follow-up period will be tabulated with exact 95% CI as follows:

- Over the 2 or 3 doses, the percentage of subjects with the symptom and its exact 95% CI.
- Over the 2 or 3 doses, the percentage of doses with the symptom and its exact 95% CI.
- At each study dose (visit), the percentage of subjects with the symptom and its exact 95% CI.

Occurrence of fever will be reported per 0.5°C cumulative increments as from  $\geq 38^{\circ}\text{C}$  as well as the occurrence of fever  $>40^{\circ}\text{C}/104^{\circ}\text{F}$  with causal relationship to the study treatment.

The verbatim reports of unsolicited symptoms will be reviewed by a physician and the signs and symptoms will be coded per the Medical Dictionary for Regulatory Activities (MedDRA). Every verbatim term will be matched with the appropriate preferred term. The percentage of subjects with unsolicited AEs within 30 days after any doses with its exact 95% CI will be tabulated by group and by MedDRA preferred term. Similar tabulation will be done for Grade 3 unsolicited AEs, for unsolicited AEs that resulted in a medically attended visit, for Grade 3 and causally related unsolicited AEs and for unsolicited AEs causally related to vaccination. These tabulations will include SOC and SOC/PT analyses.

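### SAP 5.2 groups the Exposed Set by the first product given, so if a subject receives different products at different doses, reactions after the later product are tabulated under the Dose 1 product (minor)

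*SAP*

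**What the plan says.** Protocol 9.4.2.1 sets the population for the primary safety analysis: "The primary analysis will be performed on the Exposed Set". Protocol 9.3, Table 24, gives the grouping rule for that set: "The allocation in a group is done in function of the administered treatment". It does not say which dose decides, and it has no rule for a subject who receives two products.

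SAP 5.2 contains two statements. Subjects "will be analyzed according to treatment received", and then: "The allocation in a group is done in function of the first administered treatment". The Unsolicited Safety Set, Solicited Safety Set and Subcohort Exposed Set (SAP 5.2.1 to 5.2.3) follow directly, and none has a grouping rule of its own. SAP 3.3, which lists changes from the protocol, does not mention the restriction to the first treatment.

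SAP 6.4.1 attributes events to doses: "The dose relative to an event is the most recent study dose given to a subject prior to the start of a given event". SAP 16.1 asks for solicited symptoms over all doses by subject, over all doses by dose, and by visit: "At each study dose (visit), the percentage of subjects with the symptom and its exact 95% CI".

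Mixed-product dosing is foreseen. SAP 11.2 lists "two doses not in the same treatment group" among the reasons for removal from the per-protocol immunogenicity set. Protocol 6.6.2 states: "Treatment numbers will be allocated by dose". Protocol 6.6.2.1 adds that the number issued for each later dose is consistent with the subject's allocated group.

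**The concern.** Read literally, the SAP gives each subject one group, set at Dose 1 and kept for the whole study. For a subject given another product at Dose 2 or Dose 3, the dose-specific rows report a reaction under a product that was not given at that dose. This sits badly with analysis by treatment received in the same section.

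The plan already has a rule for such subjects in the per-protocol immunogenicity analysis, which serves the secondary objective. It has none for the safety analysis, which serves the primary objective in a first-in-human trial. For a rare serious event or potential immune-mediated disease, a single event may be the whole signal, so the column it falls in matters. SAP 4.3 rules out unblinded individual listings at both interim analyses, so a reader of the Day 61 or Day 521 tables could not see that an event had been credited to the wrong product.

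**Working it through.** **Inputs.** Planned arm sizes at ages 50-70 are 30 placebo, 45 Ag and 45 Ag + AS01B (Protocol 9.2). Planned Step 4 active arms, the source of the Dose 3 subcohort, are 25 Ag and 35 Ag + AS01B (Protocol Table 10). Intervals are Clopper-Pearson (SAP 6.1). The documents give no rate of mixed-product dosing, so one such subject is assumed, with all planned subjects receiving Dose 2 and contributing data.

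**The plan's own figures.** The probability of at least one event in 45 subjects is 1 - (1 - p)^45.
- p = 0.035: 79.9%, against the stated 80%.
- p = 0.05: 90.1%, against the stated 90%.

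Exact limits for 0/45 (0-7.9%) and 1/45 (0.1-11.8%) match Protocol Table 22. This confirms only the denominators and the interval method. The plan states no figure for misattribution.

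**Do the rules regroup by product?**
1. SAP 5.2 fixes the group at the first administered treatment.
2. SAP 6.4.1 decides which dose an event follows and does not change the group.
3. SAP 5.2.1 to 5.2.3 add no grouping rule.
4. SAP 11.2 acts only on the per-protocol sets.

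So a Dose 2 event enters the Dose 2 row of the Dose 1 product's column.

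**Case A: placebo at Dose 1, Ag + AS01B at Dose 2, and a reaction no other subject has.** For zero events the upper limit is 1 - 0.025^(1/n), which gives 11.9% at n = 29. Regrouping moves one subject: 30 - 1 = 29 and 45 + 1 = 46.

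| Dose 2 table | Placebo | Ag + AS01B |
|---|---|---|
| SAP 5.2 rule | 1/30 = 3.3% (0.1-17.2%) | 0/45 = 0% (0-7.9%) |
| By product given at that dose | 0/29 = 0% (0-11.9%) | 1/46 = 2.2% (0.1-11.5%) |

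The direction of the comparison reverses. In a percentage-of-doses table over the first two doses, the SAP rule gives placebo 1/(30 × 2) = 1/60 = 1.7% and Ag + AS01B 0/(45 × 2) = 0/90. Counting each dose under its own product gives 0/59 and 1/91 = 1.1%.

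**Case B: Ag at Dose 1, Ag + AS01B at Dose 2, same assumption.**

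| Dose 2 table | Ag | Ag + AS01B |
|---|---|---|
| SAP 5.2 rule | 1/45 = 2.2% (0.1-11.8%) | 0/45 = 0% (0-7.9%) |
| By product given at that dose | 0/44 = 0% (0-8.0%) | 1/46 = 2.2% (0.1-11.5%) |

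**Dose 3.** At full planned Step 4 size, one misplaced event is 1/25 = 4.0 points in the Ag column or 1/35 = 2.9 points in the Ag + AS01B column.

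**No mixed-product subject.** Both rules give identical tables and the shift is 0.

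**The case against.** The best defence is that SAP 5.2 does what a SAP should do and fills a gap. The first administered treatment is still an administered treatment, not a randomised one. SAP 5.3 groups the Full Analysis Set by first treatment as randomised, so the two sections look like one convention anchored at the first dose. A reader might infer that the SAP breaks a dose-by-dose rule in the protocol. The documents do not support that, because Table 24 names no dose and has no mixed-product rule. What remains is the tension inside SAP 5.2, and a narrowing that SAP 3.3 does not record.

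The trigger is also a dosing error that the design guards against. Later treatment numbers follow the allocated group (Protocol 6.6.2.1), and replacement doses must match the assigned formulation (Protocol 6.5.1). Placebo recipients are excluded from Dose 3 (Protocol 4.1). A reader might take the item in SAP 11.2 as a sign that mixed dosing occurred, but it is one entry in a list of possible deviations.

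A reader might also infer that the rule makes the vaccine look safer in general. That fits placebo-to-active errors only. Case B moves an event between two active arms, and other orders act differently.

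Some protection exists elsewhere. SAP 9 calls for listings of randomisation, administration and deviations, and SAP 16.1.2 lists serious events, so a mixed-product case would be visible at the final analysis. The safety committee reviews unblinded data (Protocol 9.7), and its analyses lie outside this SAP (SAP 1), so nothing here shows an effect on the holding rules. Listings do not correct the tables, however, and unblinded ones are absent at the interims.

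Finally, by-subject cumulative tables need one group per subject, and any choice misplaces some of a mixed-product subject's doses. That part of the defence stands: for those tables the gap is the lack of a stated rule for mixed-product subjects, and no particular choice is the only correct one.

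**Conclusion.** The point holds, as a minor one. In a case the SAP itself foresees, its stated rule places a post-dose reaction under a product not given at that dose, including in tables whose purpose is to describe that dose. In Case A one event moves from the Ag + AS01B column to placebo, a change of 3.3 points in placebo and 2.2 points in Ag + AS01B. This rests on planned arm sizes, complete Dose 2 data, a literal reading of SAP 5.2, and one assumed mixed-product subject who alone has the reaction. The number of such subjects is not given and may be zero, in which case nothing changes. The documents do not support calling this a contradiction of the protocol, a bias that has occurred, or a fault in the safety committee's monitoring.

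**What to change.** Amend SAP 5.2 before the final analysis:

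- Group per-dose and percentage-of-doses safety tables by the product administered at that dose.
- State that the same rule applies to the Subcohort Exposed Set.
- Name in advance one rule for by-subject cumulative tables (overall AEs, SAEs, pIMDs). Keeping the first product received or using a hierarchy of products are both possible; the choice should be made before any such case and its events are known.
- Footnote the affected tables and list every mixed-product subject with the product and date of each dose.
- Record the grouping rule in SAP 3.3.

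The cost is a few sentences, a footnote and a listing. No new data are needed, because each administered treatment number is already recorded in the eCRF (Protocol 6.6.2, SAP 3.4). The one drawback is that a mixed-product subject may appear in different columns at different doses, so denominators can differ by one between dose rows. The footnote explains this.

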#### 5.2.1. UNSOLICITED SAFETY SET

The unsolicited safety set will contain all subjects who have received at least 1 dose of study treatment (included in the Exposed Set) that report unsolicited AEs or report not having unsolicited AEs.

#### 5.2.2. SOLICITED SAFETY SET

The solicited safety set will contain all subjects who received at least 1 dose of the study treatment (included in the Exposed Set) who have solicited safety data.

#### 5.2.3. SUBCOHORT EXPOSED SET

The subcohort exposed set will contain all subjects who have received the Dose 3 on an active arm.

## 5.3. FULL ANALYSIS SET

The full analysis set will contain all subjects who received at least 1 dose of the study treatment to which they are randomized and have postvaccination immunogenicity data.

The allocation in a group is done in function of the first treatment as per randomization.

The Full Analysis Set will be performed if the percentage of vaccinated subjects with serological results excluded from the Per-protocol Set for analysis of immunogenicity is 10% or more.

Document:	\\\usadc-nas01a\cp_ops\PROJECTS\Glaxo SmithKline\GSK208109_BZA47109\SAP		
Author:	PPD	Version Number:	3.0

Template No: CS\_TP\_BS016 – Revision 5  
Effective Date: 01Apr2018

Reference: CS\_WI\_BS005

## 5.4. PER-PROTOCOL SET

The per-protocol set will contain all subjects included in the full analysis set minus subjects with protocol deviations that lead to exclusion. The protocol deviations leading to exclusion of the subjects are described in Section 11.2. Three Per-protocol Sets for analysis of immunogenicity will be derived:

### 5.4.1. PER-PROTOCOL SET FOR ANALYSIS OF IMMUNOGENICITY AT DAY 61

The analysis set will contain all subjects included in the Per-protocol Set, with no protocol deviations leading to exclusion until Day 61 and with at least 1 immunogenicity data available at Day 61.

### 5.4.2. PER-PROTOCOL SET FOR ANALYSIS OF IMMUNOGENICITY AT DAY 180

The analysis set will contain all subjects included in the Per-protocol Set, with no protocol deviations leading to exclusion until Day 180 and with at least 1 immunogenicity data available at Day 180.

### 5.4.3. PER-PROTOCOL SET FOR ANALYSIS OF IMMUNOGENICITY AT DAY 390

The analysis set will contain all subjects included in the Per-protocol Set, with no protocol deviations leading to exclusion until study end (Day 390) and with at least 1 immunogenicity data available at Day 390.

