### 4.3. INTERIM ANALYSIS

A first analysis will be performed when all data up to Day 61 (ie, data that are as clean as possible) are available. The immunogenicity data available until Day 61, and the safety and reactogenicity data available at the time of this analysis will be summarized based on unblinded treatment groups. At this point, the IQVIA statistical team, including those responsible for creating the programs to produce the outputs for the Interim Analysis, will be unblinded for the analysis (ie, will have access to individual subject treatment assignments). Whenever it is needed after the interim analyses, the GSK statistical team may have access to individual subject treatment and data.

The remaining study personnel will stay blinded (ie, will not have access to the individual subject treatment assignment) until study end. It is possible however, due to the limited sample size, that unblinding occurs for a few subjects having a specific AE or SAE (eg, an AE/SAE occurring only in a single group). Therefore, anyone having access to the analysis of Day 61 could become unblinded regarding those specific cases. The study will be considered as partial-blind from this point onwards. Subjects will be provided with information about the study arm, via the investigator at the study end.

Note: In a partial-blind study, the subject, the investigator, or anyone assessing the outcome is aware

Document:	\usadc-nas01a\cp_ops\PROJECTS\Glaxo SmithKline\GSK208109_BZA47109\SAP		
Author:	PPD	Version Number:	3.0
		Version Date:	27SEP2021

Template No: CS\_TP\_BS016 – Revision 5  
Effective Date: 01Apr2018

Reference: CS\_WI\_BS005

of the assignment in at least one treatment group but unaware of the treatment assignment(s) in one or more other treatment groups. Individual listings will be provided at the study end to the investigator.

The second interim analysis will be performed when all data up to 1 month after Dose 3, ie, Day 521 (ie, data that are as clean as possible) are available. The immunogenicity data available until Day 521, and the safety and reactogenicity data available at the time of this analysis will be described. No individual listings will be provided.

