## 5.5. SUBCOHORT PER-PROTOCOL SET

### 5.5.1. SUBCOHORT PER-PROTOCOL SET FOR ANALYSIS OF IMMUNOGENICITY AT DAY 521

The analysis set will contain all subjects included in the Per-protocol Set, who received the Dose 3 on an active arm, with no protocol deviations leading to exclusion until Day 521 and with at least 1 immunogenicity data available at Day 521.

### 5.5.2. SUBCOHORT PER-PROTOCOL SET FOR ANALYSIS OF IMMUNOGENICITY AT DAY 670

The analysis set will contain all subjects included in the Per-protocol Set, who received the Dose 3 on an active arm, with no protocol deviations leading to exclusion until Day 670 and with at least 1 immunogenicity data available at Day 670.

Document:	\\\usadc-nas01a\cp_ops\PROJECTS\Glaxo SmithKline\GSK208109_BZA47109\SAP		
Author:	PPD	Version Number:	3.0
		Version Date:	27SEP2021

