## 5.6. COVID-19 SET

The analysis set will contain all subjects included in the exposed set who were not able to go to the site for the Visit 5 (Day 61) on schedule, due to study being paused during COVID-19, and as a result, had their immunogenicity samples collected outside of the protocol specified interval. This analysis set will be used for additional descriptive summaries of immunogenicity variables.

Analysis	Enrolled Set	Exposed Set	Un-solicited Safety Set*	Solicited Safety Set	Full Analysis Set**	Per-protocol (PP) Set		Subcohort PP Set		COVID-19 Set
						PP Set Day 61	PP Set Day 180	PP Set Day 390	PP Set Day 521	
Subject Disposition	✓									
Baseline Assessments		✓	✓			✓	✓	✓	✓	✓
Concomitant Medications		✓								
Exposure		✓								
Immunogenicity Analysis					✓	✓	✓	✓	✓	✓
Protocol Deviations		✓								
Adverse Events			✓	✓						
Other Safety (lab, vitals)		✓								

\* The safety/reactogenicity analysis will be first performed on the exposed set. If  $\geq 10\%$  of subjects have missing information for unsolicited symptoms, then the analyses on the unsolicited safety set will be performed.

\*\* Analysis in this set will be performed if the percentage of vaccinated subjects with serological results excluded from the Per-protocol Set for analysis of immunogenicity is 10% or more

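### As written, a late or failed Day 61 sample also removes a subject's valid Day 180 to Day 670 results from the per-protocol immunogenicity sets

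*SAP*

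**What the plan says.** SAP 5.4 defines a parent set with no date limit: "The per-protocol set will contain all subjects included in the full analysis set minus subjects with protocol deviations that lead to exclusion". The Day 61, 180 and 390 sets are drawn from that parent, and each adds its own cutoff. The Day 61 set takes parent members "with no protocol deviations leading to exclusion until Day 61 and with at least 1 immunogenicity data available at Day 61"; the Day 180 set repeats the pattern, "with no protocol deviations leading to exclusion until Day 180". SAP 5.5 builds the Day 521 and Day 670 sets in the same way: "The analysis set will contain all subjects included in the Per-protocol Set, who received the Dose 3 on an active arm", again with a cumulative cutoff.

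SAP 11.2 gives a non-exhaustive list of deviations that eliminate a subject from the per-protocol set. Two concern samples: "interval between post vaccination blood sampling and previous dose" and "serology result at post vaccination dose 2 not available for all assays". Neither names the set to which it applies. The complete list of codes is in the Protocol Deviation Management Plan (PDMP), which is not among the documents.

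Three other provisions bear on this:
- SAP 15 (also Protocol 9.4.3) adds a Full Analysis Set (FAS) analysis if exclusions reach 10% in any study group.
- SAP 5.6 defines a COVID-19 Set for subjects whose Day 61 visit was delayed by the study pause and who "had their immunogenicity samples collected outside of the protocol specified interval". It is used for extra descriptive summaries.
- Protocol 8.11 says that the effect of a late sample in special circumstances on the per-protocol set is judged case by case.

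**The concern.** A blood draw that is late at Day 61 tells us nothing wrong about an in-window draw at Day 180 or Day 521. The same is true of an assay that failed at Day 61. A dosing error, an eligibility violation or an immune-altering event is different, because it can affect every later titer. The SAP treats both kinds alike, as whole-subject eliminations that carry forward.

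The per-protocol set is the primary population for immunogenicity. The rule therefore affects the persistence estimates (Days 180 and 390) and the post-Dose 3 estimates (Days 521 and 670) that Amendment 03 was written to obtain, in a subcohort that is already small. No hypotheses are tested (Protocol 9.1), so the precision of these estimates is the main thing that the immunogenicity analysis delivers.

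The undated parent raises a second question: whether a deviation after Day 61 also removes a valid Day 61 result. If it does, the Day 61 set could shrink between the first interim and the final analysis, when SAP 4.4 has all previous analyses reproduced.

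**Working it through.** **1. The carry-forward follows from the text by two routes.**
- Through the parent: a late Day 61 draw is on the SAP 11.2 list, so the subject leaves the parent set. All five dated sets are subsets of the parent.
- Through the cutoffs: even without the parent, a deviation at Day 61 lies before Days 180, 390, 521 and 670 and so counts against each of those sets.

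**2. The post-dose-2 serology code.** If it means that no assay result is available, it adds nothing at Day 61, because SAP 5.4.1 already requires one result there; its only effect is on other timepoints. If it means that not every assay result is available, it conflicts with SAP 5.4.1, which accepts a single result. Either way it needs rewording.

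**3. Backward loss.** The undated parent says that a Day 521 deviation removes the Day 61 result. The Day 61 cutoff in SAP 5.4.1 implies that it does not, and has no function if the parent has already removed the subject. Both readings are available, and two programmers could build different sets.

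**4. The plan's own precision figure.** Protocol 9.2 assumes 45 per active arm, 20% nonevaluable and log10 SDs of 0.84 (Toxin A) and 1.4 (Toxin B).
- 45 × 0.80 = 36 evaluable.
- CI = GMFR × 10^(± t(0.975, n−1) × SD/√n).
- At GMFR 10 and n = 36 this gives [5.20; 19.24] for Toxin A and [3.36; 29.76] for Toxin B. Table 23 has [5.20; 19.23] and [3.36; 29.79], so it reproduces to rounding.

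**5. Illustration for the main arms.** The documents give no per-visit deviation rate. Assume a rate q of sample-level deviations, independent across Days 61, 180 and 390, with 45 per arm. Visit-specific sets keep 45(1−q) at each visit. Cumulative sets keep 45(1−q)² at Day 180 and 45(1−q)³ at Day 390. The 7.2% row uses q = 1 − 0.8^(1/3), which spreads the plan's 20% over three visits. Intervals are Toxin B at GMFR 10, with n rounded.

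| q | Visit-specific n | Cumulative n, Day 180 | Cumulative n, Day 390 | CI, visit-specific | CI, cumulative Day 390 |
|---|---|---|---|---|---|
| 2% | 44.1 | 43.2 | 42.4 | [3.75; 26.65] | [3.66; 27.31] |
| 5% | 42.8 | 40.6 | 38.6 | [3.71; 26.97] | [3.52; 28.43] |
| 7.2% | 41.8 | 38.8 | 36.0 | [3.66; 27.31] | [3.36; 29.76] |
| 10% | 40.5 | 36.5 | 32.8 | [3.61; 27.66] | [3.19; 31.36] |

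If the undated parent is applied literally, the Day 390 counts hold at every visit, Day 61 included.

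**6. Illustration for the Dose 3 subcohort.** Protocol Table 21 expects about 50 subjects at Days 521 and 670. Split 35:25 as in Step 4, that is 50 × 35/60 ≈ 29 AS01B and 50 × 25/60 ≈ 21 Ag. The split and a 20-30% loss are assumptions. The Toxin B CI factor is 10^(t(0.975, n−1) × 1.4/√n):
- AS01B: n = 29 gives 3.41; n = 23 (20% lost) gives 4.03; n = 20 (30% lost) gives 4.52.
- Ag: n = 21 gives 4.34; n = 15 (30% lost) gives 5.96.

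**7. When the FAS fallback starts.** With 45 in a group, 4 exclusions are 4/45 = 8.9% (no FAS analysis) and 5 are 5/45 = 11.1% (FAS analysis). Four exclusions that all fall among the 29 AS01B Dose 3 subjects are 4/29 = 13.8% of them, yet do not reach the trigger if it is assessed on the whole arm.

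**The case against.** **The FAS fallback covers it.** In part. Losing 6 of 29 AS01B subjects is 6/45 = 13.3% of the full arm, so the 20-30% scenario would trigger a FAS analysis. But the per-protocol set stays primary, the FAS readmits every other deviation as well, and below 10% nothing is restored. No subcohort FAS is defined, and SAP 15 bases the Dose 3 analysis on the Subcohort Per-protocol Set.

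**COVID delays are not removed automatically.** This stands. The only late Day 61 samples that the documents describe come from the COVID pause, and Protocol 8.11 leaves those to judgement. It gives no criterion, however, and does not cover ordinary late samples. The COVID-19 Set adds a summary; it does not return subjects to the per-protocol estimates.

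**Case-by-case exclusion of data, not subjects, is already allowed.** SAP 11.2 attaches that wording to immune conditions and concomitant products. The two sample-level deviations are in the separate elimination list.

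**Dose 3 required all visits to Visit 7.** This stands for a missed Day 61 visit, which leaves no Day 521 or 670 data to lose. It does not help a subject with a late draw or a failed assay.

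**The PDMP may limit the codes to a timepoint.** Possibly; it cannot be checked here. The SAP text should agree with it in any case.

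**Cumulative exclusion is a conservative choice.** Fair for dosing, eligibility and immune-altering deviations, and the fix keeps it for those.

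Two stronger readings are tempting. One is that later deviations definitely delete Day 61 results; the dated cutoffs contradict that, so it is only an ambiguity. The other is that exclusions are decided by unblinded staff, because SAP 4.3 says that "the GSK statistical team may have access to individual subject treatment and data" after the interim analyses. That sentence permits access; it does not say that those staff decide exclusions. SAP 11.2 gives its case-by-case decisions to the study team, and SAP 4.3 keeps study personnel outside the statistical teams blinded.

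**Conclusion.** The point holds for carry-forward loss. As the SAP is written, an ordinary late Day 61 draw or a failed Day 61 assay removes valid later results from the primary immunogenicity sets, and no safeguard reliably puts them back. Backward loss of Day 61 results is an ambiguity to settle, not an established rule.

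The number of subjects affected cannot be derived from the documents. The subcohort illustration widens the Toxin B factor for AS01B from 3.4 to 4.0-4.5, but it rests on an assumed 35:25 split, an assumed 20-30% rate and exclusion of every affected subject. In the main arms the effect is modest at the low rates in the table. Immunogenicity is a secondary, descriptive objective, so this should be corrected but does not threaten the primary safety analysis.

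**What to change.** - Remove the undated parent. Define each dated set directly from the FAS: no dosing, eligibility or immune-altering deviation up to that visit, and a valid in-window result at that visit. For Days 521 and 670, add receipt of Dose 3. This also settles the backward-loss ambiguity.
- In SAP 11.2, state that sampling-interval and missing-result deviations exclude only the affected timepoint.
- Limit the post-dose-2 serology code to the Day 61 set and align it with the one-result requirement in SAP 5.4.1.
- State the criterion for case-by-case decisions on special-circumstance delays.
- Make the PDMP codes match.

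The cost is SAP wording and a visit-level flag in the analysis dataset. The number of subjects will vary by visit, and tables must show it.
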